#### 5.3 Safety Population

The Safety population will consist of all subjects who receive randomized study treatment. The Safety population will be used for summaries of safety parameters. Subjects will be analyzed according to treatment received. Any subject receiving at least 1 dose of CPNA during the study (not including food product administered during DBPCFC) will be categorized in the CPNA treatment group, regardless of randomization assignment.

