## **10.3** Adverse Events

All reported adverse events (AEs) will be classified into System Organ Class (SOC) and Preferred Term (PT) using Medical Dictionary for Regulatory Activities (MedDRA) version 16.0. A summary of SOC, PT, and verbatim term will be provided.

Treatment-emergent adverse events (TEAEs) are defined as any event starting during or after the active treatment period. Any event occurring on the same day as a DBPCFC or in-clinic escalation dosing will be considered to be associated with those events, and flagged as such in the listings. Events will be classified by onset time with regards to time of last dose (within 2 hours of last dose, > 2 hours since last dose, and unknown time since last dose).

Events will be further classified by time period of onset, as follows:

- *Pre-study*: All events beginning prior to first dose of Screening DBPCFC; if times are unavailable, any event prior to the first day of Screening DBPCFC.
- Screening DBPCFC: All events beginning after the first dose of the food challenge during the Screening DBPCFC, and within 24 hours of the last dose of that food challenge and prior to the first dose of randomized treatment. If times are not available, any event starting on the same day as any part of the Screening DBPCFC will be categorized as Screening DBPCFC.
- Pre-treatment: All events beginning more than 24 hours after the last dose of the Screening DBPCFC but before the first dose of randomized treatment. If the two halves of the food challenge are more than 24 hours apart, events that begin more than 24 hours after the end of the first half, but prior to the start of the second half, will be categorized as Pre-treatment. If times are not present, events beginning on any day after the first day of Screening DBPCFC, and before Visit 01 Day 1, excluding any day on which Screening DBPCFC is administered, will be Pre-treatment.
- Visit 01: All events beginning on or after the first dose on Visit 01 Day 1, and within 24 hours of the last dose administered at Visit 01 (Days 1, 2, or 3); if times not present, events beginning on the same date as any day of Visit 01.
- *Up-dosing Visit*: All events beginning on or after the increased dose administered and within 24 hours of that dose; if times not present, events

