beginning on the same date as a dose increase. If the same dose level, or a decreased dose level, is administered at a scheduled up-dosing visit, an event within 24 hours of that dose or on that day will be classified as On-treatment, unless there had been a higher dose administered within that 24 hour period or on that day, respectively.

- On-treatment: All other events beginning after the first dose of randomized treatment and prior to the Exit DBPCFC, or within 24 hours of the last dose of randomized study treatment if an Exit DBPCFC is not performed or is >24 hours after the last dose. If times are not available, any event starting during the active treatment period, but not on the same day as Visit 01 or an Up-dosing visit, will be On-treatment.
- *Exit DBPCFC*: All events beginning after the first dose of product was administered during the Exit DBPCFC, and within 24 hours of the last dose of that food challenge. If times are not available, any event starting on the same day as any part of the Exit DBPCFC will be categorized as Exit DBPCFC.
- *Post-Exit DBPCFC*: All events beginning more than 24 hours after the Exit DBPCFC. If the two halves of a food challenge are more than 24 hours apart, events that begin more than 24 hours after the end of the first half, but prior to the start of the second half, will be categorized as Post-Exit DBPCFC.
- Post-treatment: All events beginning >24 hours after the last dose and prior to the Exit DBPCFC if an Exit DBPCFC is performed, or >24 hours after the last dose if an Exit DBPCFC is not performed. If times are not available, all events beginning on or after the day after the last part of the Exit DBPCFC (if performed) or the day after the last dose of randomized treatment (if no Exit DBPCFC performed) will be categorized as Post-treatment. If the two halves of the Exit DBPCFC are more than 24 hours apart, events that begin more than 24 hours after the end of the first half, but prior to the start of the second half, will be categorized as Post-treatment.

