Listings will be provided for all adverse events; serious adverse events (SAEs); severe, life-threatening, or fatal adverse events; adverse events leading to death; adverse events leading to permanent withdrawal of study treatment; adverse events related to study treatment; and adverse events occurring within 2 hours of the last dose of randomized study treatment. Listings of both adverse events associated with DBPCFC, and SAEs associated with DBPCFC, will be provided. A separate listing of all adverse events, sorted by time period of onset, will also be provided; and SAEs will be flagged.

An overall summary of frequencies of types of adverse events (TEAEs, SAEs, etc.) will be provided. An additional summary table of all TEAEs by Preferred Term, in order of descending frequency, will also be provided.

Summaries of adverse events by time period, SOC, and PT will be provided for TEAEs, treatment-emergent SAEs, and TEAEs related to study treatment. Subjects will be counted at most one time per time period overall, at most one time per SOC and at most one time per PT for these summaries. Summary tables will be sorted in order of time period (overall, then chronological), descending overall frequency of SOC and PT, with alphabetical sorting for ties. The number of subjects at risk for each time period (i.e., the number of subjects on study at the beginning of each time period) will be used as the denominator. In other words, the number of subjects in the Safety population will be used as the denominator for the Overall, On-treatment, and Post-Treatment time periods, the number of subjects undergoing Visit 01 will be used as the denominator for Visit 01, the number of subjects with 1+ updosing visits will be used as the denominator for Updosing Visit, the number of subjects undergoing the Exit DBPCFC will be used as the denominator for the Exit DBPCFC, Post-Exit DBPCFC time points.

Events related to study treatment are defined as those classified as possibly, probably, or definitely related to study treatment. If relationship is missing, the event will be conservatively be summarized as being related to study treatment.

Event severity is classified as mild, moderate, severe, life-threatening, or death. If severity is missing, a separate category of missing severity will be included in the summary table, and no imputation of severity will be performed.

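### SAP 10.3 divides Post-treatment adverse events by the whole Safety population, against its own at-risk rule, although with timed onsets almost only subjects without an Exit DBPCFC can be in that period

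*SAP*

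**What the plan says.** SAP 10.3 sorts adverse events by period of onset and summarizes them by period (Tables 14.3.1.2 to 14.3.1.6). It first gives a general rule for the denominator: "The number of subjects at risk for each time period (i.e., the number of subjects on study at the beginning of each time period". The next sentence, offered as a restatement of that rule, is a fixed list in which "the number of subjects in the Safety population will be used as the denominator for the Overall, On-treatment, and Post-Treatment time periods". The other periods in the list are limited to subjects who enter them: those with Visit 01, those with at least one up-dosing visit, and, for the challenge, "the number of subjects undergoing the Exit DBPCFC will be used as the denominator for the Exit DBPCFC, Post-Exit DBPCFC time points". SAP 5.3 defines the population: "The Safety population will consist of all subjects who receive randomized study treatment".

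The period definitions in the same section decide who can be counted where:

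- Visit 01 takes events "within 24 hours of the last dose administered at Visit 01 (Days 1, 2, or 3").
- On-treatment takes "All other events beginning after the first dose of randomized treatment and prior to the Exit DBPCFC". It ends 24 hours after the last dose if there is no challenge, or if the challenge comes later than that.
- Post-treatment, onset time known: for a challenged subject, "All events beginning >24 hours after the last dose and prior to the Exit DBPCFC if an Exit DBPCFC is performed". For a subject without a challenge, everything from 24 hours after the last dose.
- Post-treatment, onset time missing: for a challenged subject, "all events beginning on or after the day after the last part of the Exit DBPCFC (if performed").
- Post-Exit DBPCFC takes events starting more than 24 hours after the challenge. It has no rule for missing times.
- If the two halves of the Exit DBPCFC are more than 24 hours apart, events in the gap are assigned to both Post-Exit DBPCFC and Post-treatment.

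The February 2015 addendum changes neither the denominators nor the period definitions.

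**The concern.** The rule and the list agree only where every treated subject enters the period. For Post-treatment that is not so. A subject who has the Exit DBPCFC spends the time after it in Post-Exit DBPCFC. The list restricts Post-Exit DBPCFC to challenged subjects but does not restrict Post-treatment to the remaining subjects, so two neighbouring periods are reported on different bases.

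Subjects without an Exit DBPCFC do have a real Post-treatment window. Protocol 6.5 brings them back 14 days after the last dose, and Protocol 7.6 follows adverse events for up to 30 days after treatment ends. This period is where a reader would look for what happened to subjects who stopped early, including those who stopped for symptoms. Their percentage would be diluted by completers whose corresponding time is counted elsewhere.

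SAP 11.1 makes a useful comparison. For epinephrine use it merges the time after treatment and after the Exit DBPCFC into one period, which nearly all subjects can enter, and it uses subjects at risk. SAP 10.3 splits that period but adjusts only one of the two denominators.

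**Working it through.** **Step 1: the plan's own figures.** The documents give no adverse event percentage. The inputs come from SAP 4: about 50 subjects, 1:1, hence 25 per arm, with 3 or 5 per arm not undergoing the Exit DBPCFC.

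- 3/25 = 12% and 5/25 = 20%, as stated.
- 0.25 × 22/25 = 22% and 0.25 × 20/25 = 20%, the stated effective placebo rates. So 25 per arm is the plan's base.

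I assume that all 25 are dosed, so that the Safety population is 25 per arm.

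**Step 2: who can be in Post-treatment when onset times are known.** Dosing is daily, and SAP 3.2.3 schedules no dose on the day of Visit 03. The last dose before the challenge is therefore normally taken the day before, and the stretch from 24 hours after it to the challenge is nil or a few hours. The only other entry for a challenged subject is a gap of more than 24 hours between challenge halves. Every other later event goes to the Exit or Post-Exit period. The number at risk, k, is thus close to the number without an Exit DBPCFC.

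**Step 3: size for Post-treatment.** For one affected subject, the printed percentage is 1/25, the at-risk percentage is 1/k, and the understatement factor is 25/k.

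| k per arm | Source | Printed | At risk | Factor |
|---|---|---|---|---|
| 3 | SAP 4 | 4.0% | 33.3% | 8.3 |
| 5 | SAP 4 | 4.0% | 20.0% | 5.0 |
| 8 | assumed | 4.0% | 12.5% | 3.1 |
| 10 | assumed | 4.0% | 10.0% | 2.5 |

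**Step 4: missing onset times.** An untimed event after the challenge falls into Post-treatment, so completers can contribute to it. If every onset time were missing, k would approach 25 and the factor would approach 25/25 = 1. The documents do not say how many times will be missing. The factors in Step 3 are therefore the values for complete timing.

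**Step 5: On-treatment.** The period starts after the first dose, and everyone in the Safety population has been dosed. Only subjects who stop at Visit 01 have no time in it: their first 24 hours after the last dose count as Visit 01 and the rest as Post-treatment. With f such subjects per arm (assumed, since the documents give no expected number), the factor is 25/(25 − f):

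| f | Factor | 10 affected: printed | 10 affected: at risk |
|---|---|---|---|
| 0 | 1.00 | 40.0% | 10/25 = 40.0% |
| 1 | 1.04 | 40.0% | 10/24 = 41.7% |
| 2 | 1.09 | 40.0% | 10/23 = 43.5% |
| 3 | 1.14 | 40.0% | 10/22 = 45.5% |

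**The case against.** The best defence has four parts.

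- **Completers are not shut out of Post-treatment.** The missing-time rule and the gap between challenge halves both place some of their events there. This stands, and it makes the 5-fold and 8.3-fold figures conditional on known onset times. It does not justify the list: the same post-challenge event is Post-Exit if timed and Post-treatment if untimed, which is a further inconsistency to repair.
- **The denominators are named explicitly, and percentages of all treated subjects are a recognized convention.** The programming is indeed unambiguous if the list is followed. But the SAP does not present these as percentages of all treated subjects; it presents them as percentages of subjects at risk.
- **The tables are descriptive.** SAP 10.3 specifies no test on them, the Overall denominator is right, and a listing shows every event by period. This limits the consequence, and I accept it.
- **On-treatment is essentially correct.** This stands too. A reader might infer from the shared wording of the list that On-treatment percentages are diluted in the same way, but Step 5 shows at most a small effect.

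A reader might also infer that the dilution differs by arm, on the ground that escalation failures would be mainly CPNA subjects. The documents do not support a figure for that. The sample size section assumes equal numbers without an Exit DBPCFC in each arm, so the point should not rest on it.

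**Conclusion.** The Post-treatment denominator is wrong as written, because it contradicts the at-risk rule that it claims to restate. On the plan's own 3 or 5 of 25 subjects per arm without an Exit DBPCFC, the printed percentage is too low by a factor of 8.3 or 5. This assumes known onset times, 25 treated subjects per arm, and negligible Post-treatment time among completers. The factor falls towards 1 as more onset times are missing, so it should not be read as unconditional.

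For On-treatment the only correction is for subjects who stop at Visit 01, a factor of 1.00 to 1.14 for an assumed 0 to 3 per arm. The consequence is confined to the descriptive by-period summaries. It is still worth correcting, because those summaries cover serious, related and severity-graded events in subjects who stopped early.

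**What to change.** 1. **Give each event one period.** Put completers' post-challenge events in Post-Exit DBPCFC whether or not they are timed. Assign the gap between Exit challenge halves to one period only; Post-Exit DBPCFC fits the denominator in item 2, since completers would otherwise add events to Post-treatment without being counted in it. Assign any short interval between 24 hours after the last dose and the Exit DBPCFC to On-treatment.
2. **Post-treatment denominator.** Use subjects without an Exit DBPCFC who remain on study more than 24 hours after the last dose. A flag for any time at all under the present Post-treatment definition would not do: completers with a few hours before the challenge would re-enter, and the denominator would depend on the clock time of the challenge.
3. **Other denominators.** Keep the Safety population for Overall. Subjects who stop at Visit 01 can be dropped from On-treatment.
4. **Display.** Print the at-risk number by arm and period in each by-period table.

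The cost is a short edit to the period definitions and the denominator sentence in SAP 10.3, plus a derived at-risk flag. No new data are needed.

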# **10.4 Food Allergy Episodes**

The occurrence of a safety event associated with accidental food ingestion will be reported as a food allergy episode, as per Section 7.2 of the protocol. Any such event that meets the definition of an SAE will also be reported as an adverse event. All reported food allergy episodes will be listed by subject. Episodes of allergic reaction associated with foods other than peanut (as determined prior to database lock, as described in Section 12) will be flagged.

The number of subjects experiencing any food allergy episode, the number of subjects experiencing a food allergy episode in response to peanut, the number of episodes of each (peanut-related and non-peanut related) experienced per subject, and the total number of food allergy episodes will be summarized. The number of episodes with unscheduled clinic visits, treatment administered, or considered SAEs will also be summarized.

The rate of food allergies and those with unscheduled clinic visits, treatments administered, or considered SAEs will be calculated by dividing the total numbers of events by the number of subjects in that treatment group. These rates will similarly be summarized by randomized treatment group and overall.

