7.2 Food Allergy Episodes

In order to report the occurrence of a safety event associated with accidental food ingestion, subjects will be instructed to contact the site study coordinator or investigator

for any adverse event. The subject may be asked to return to the site. These events will be reported as follows:

- A Food Allergy Episode form will be completed for each of these events in addition to events where consumption of peanut without a reaction occurs.
- If the accidental food ingestion safety event meets the definition of a serious adverse event, as defined below, the AE/SAE form will be completed as well.

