## 3.2.2 Treatment Period (Visits 01, 02 and Up-dosing Visits)

The treatment up-dosing phase will start with an initial escalation (Visit 01) at the study center, followed by up-dosing for approximately 24 weeks, conducted in a double-blind fashion. Up-dosing will continue until the subject reaches a steady dose of 300 mg/day, is unable to continue escalation due to symptoms, or withdraws from the study. If a subject does not require any dose reductions during the up-dosing phase, the target maintenance dose of 300 mg/day will be reached in either approximately 18 or 20 weeks, depending on whether up-dosing was started at 6.0 or 3.0 mg/day, respectively. Once achieved, the target dose of 300 mg/day is to be maintained for 2 weeks, for a total of approximately 20 or 22 weeks of dosing after the initial escalation visit. If, however, a subject does require dose reductions during the up-dosing phase, the total duration of dosing after Visit 01 may be extended up to an additional 12 weeks, for a total duration of up to 34 weeks.

During Visit 01 (comprising 2 or 3 days), doses will be delivered at 20 to 30 minute intervals, as described in Table 3.2. Subjects who are unable to tolerate a dose of 3.0 mg at the end of Day 1 will be considered an initial day escalation failure. All subjects who tolerate a dose of at least 3.0 mg on Day 1 will return on Day 2 to receive their MTD (3 mg or 6 mg) under direct observation. Subjects with either no symptoms or mild symptoms on Day 2 at either 3 mg or 6 mg may start daily dosing at their highest tolerated level, and will not be required to return for Day 3.

Subjects who experience moderate or severe symptoms after receiving a 6 mg dose on Day 2 will return on Day 3 to receive the next lower dose (3 mg) under direct observation. If the 3 mg dose is tolerated, subjects return home on that dose for 2 weeks until the next escalation. Subjects with moderate or severe symptoms at 3 mg on either Day 2 or Day 3 will be considered escalation failures.

Future dose escalations will occur every 2 weeks with the initial dose increase administered in the Clinical Research Center.

Initial Days 1 to 3 (Visit 01) Escalation Schedule					
		Cumulative Study			
	Study Product Dose	Product Dose			
Dose #	(mg peanut protein	(mg peanut protein			
	or placebo)	or placebo			
1	0.5	0.5			
2	1.0	1.5			
3	1.5	3.0			
4	3.0	6.0			
5	6.0	12.0			

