## 3.2.3 Exit Visit (Visit 03)

After approximately 24 weeks of randomized study treatment, eligible subjects who reach the targeted daily dose of 300 mg/day and maintain that dose for 2 weeks will undergo an Exit DBPCFC of up to 600 mg (1043 mg cumulative) peanut protein and placebo (see Section 6.6.2 of protocol). Subjects who have not reached 300 mg/day by Week 24 will continue to up-dose as tolerated until they are eligible for the Exit DBPCFC (after 2 weeks of at-home dosing with 300 mg/day). The Exit DBPCFC will be conducted in a manner similar to the Screening DBPCFC but with the dosing schedule as shown in Table 3.4. Note also that subjects are not scheduled for a dose of study product at home or in-clinic on the day of Visit 03.

Subjects who fail escalation, whose dose escalation is halted, and/or who prematurely discontinue treatment, will return to the site for an Early Discontinuation visit that consists of the same procedures as the Exit visit, but without a DBPCFC or associated optional blood draws. An Early Discontinuation visit is to occur 14 days from the last dose of study product.

Table 3.4. PRACTALL Exit DBPCFC

Challenge Doses					
	Peanut flour with				
Peanut Protein	50% protein content				
(mg)	(mg)				
3	6				
10	20				
30	60				
100	200				
300	600				
600	1200				

The schedule of study assessments will be as follows:

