# **11 EXPLORATORY ANALYSES**

#### **11.1 Epinephrine Use as Rescue Medication**

Epinephrine use is defined as any rescue medication with a preferred name of 'EPINEPHRINE' when coded as described in Section 10.2, and with documentation of administration to a subject on a specific date.

All subjects, per protocol, are required to have epinephrine autoinjectors for use in case of a suspected anaphylactic reaction occurring outside of the clinic. There are, however, differences in how, and even if, physicians record the prescription of epinephrine autoinjectors for as-needed (PRN) use. As a consequence of this, the presence or absence of a PRN prescription for epinephrine cannot be taken to indicate epinephrine usage, regardless of whether the prescription was written prior to, or after, enrollment in the study. What is important is to be able to quantitate the number of subjects receiving doses of epinephrine and the number of doses. As epinephrine should only be administered to treat a discrete allergic reaction, each dose of epinephrine should be closely temporally associated with a specific safety event. In cases where a PRN epinephrine prescription is issued after the start of study-product dosing, the sites are queried as to if, and when, epinephrine was actually administered and to treat what specific event.

Epinephrine use will be categorized by the following time points, based on epinephrine use on the same day(s) as any of the following events:

- Any use on the same date as an accidental exposure (defined as a recorded food allergy episode) occurring on or after the first dosing date of randomized treatment
- Screening DBPCFC, further categorized into
  - Peanut Challenge: if epinephrine is administered on the day of a peanut challenge, the default assumption will be that the epinephrine administration was in response to a peanut-related event, regardless of whether a placebo challenge was also conducted on the same day)
  - Placebo Challenge
- Post Screening DBPCFC, Prior to Randomized Study Treatment
- Visit 01 (including all days of that visit)
- Up-dosing Visit (including any day in which dose is increased)
- On-Treatment (any day during the active treatment period, excluding Visit 01 and Up-dosing Visits)
- Exit DBPCFC, further categorized into
  - Peanut Challenge (with same provisos as for Screening DBPCFC)
  - Placebo Challenge

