# **12 PRE-DATABASE LOCK DATA DETERMINATION**

The purpose of the pre-database lock blinded data review is the assignment of subjects to their appropriate study populations (ITT, mITT, PP), the classification of their responder status (Responder or Non-responder), and the designation of their response subcategory (for Responders - Passed Exit DBPCFC or *Ad libitum* peanut consumption; for Non-responders - Failed Exit DBPCFC, Reached 300 mg/day but Exit DBPCFC was not conducted, or Escalation Failure). The following items (listed below) will be finalized based on blinded data review, prior to database lock and unblinding. This blinded data review will be performed by study personnel who are blinded to all subject treatment assignments, as described in Section 7.7. The team involved in making these determinations and final index of listings reviewed by the team will be documented. Each of the items will be finalized and documented prior to database lock.

- Protocol violations, as described in Section 7.5, will be classified as major violations or minor violations.
- List of exclusions from analysis populations as described in Section 5. All subjects who were randomized but not included in 1 or more analysis populations (other than the Enrolled and Screening DBPCFC Only populations) will be reviewed.
- Responder status, as described in Section 6.10, will be reviewed and compared to disposition information (reasons for early discontinuation and reasons Exit DBPCFC not done), protocol violations, and adverse events to ensure correct classifications. Overall responder status, response subcategory, and reason for missing Exit DBPCFC, as described in Sections 6.9 and 6.10, will be finalized.
- Subjects who have added *ad libitum* peanut consumption to their diet and also had additional reasons for missing the Exit DBPCFC will have imputation rules for MTD of peanut determined on a case-by-case basis. If any subjects meet these criteria, the imputation rules and justification will be documented.
- Food allergy episodes will be reviewed and categorized as peanut-related or non-peanut related.

The listings displayed in Table 11.1 will be provided for the blinded data review, with randomized treatment group and subject identifiers masked as described in Section 6.13.

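### SAP 10.4 reports food allergy episodes per subject although follow-up ranges from about 2 to 36 weeks, and it does not say whether reaction-free peanut consumption is counted

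*SAP*

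**What the plan says.** **Denominator.** SAP 10.4 calculates the rate of food allergy episodes, and of those with an unscheduled visit, treatment or SAE status, by "dividing the total numbers of events by the number of subjects in that treatment group". No time at risk enters.

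**Follow-up.** This depends on the course of dosing:
- Subjects who fail the initial escalation stop dosing at Visit 01. For anyone who stops early, "An Early Discontinuation visit is to occur 14 days from the last dose of study product" (SAP 3.2.3).
- A subject with no dose reductions reaches and holds the target dose "for a total of approximately 20 or 22 weeks of dosing after the initial escalation visit" (SAP 3.2.2).
- A subject whose escalation is halted after Visit 01 but before Week 24 is dosed to Week 24 and seen 14 days later (Protocol 3.2).
- A subject whose up-dosing is prolonged can have the Exit Visit as late as Week 36 (Protocol 6.8.4).

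**Numerator.** SAP 10.4 opens with "The occurrence of a safety event associated with accidental food ingestion will be reported as a food allergy episode" and cites Protocol 7.2. That section says: "A Food Allergy Episode form will be completed for each of these events in addition to events where consumption of peanut without a reaction occurs". For epinephrine use, SAP 11.1 treats any recorded food allergy episode as an accidental exposure. Of the blinded review before database lock, SAP 12 says only that "Food allergy episodes will be reviewed and categorized as peanut-related or non-peanut related".

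**Window.** SAP 10.4 gives no start or end date for counting episodes. SAP 11.1 restricts accidental exposures to those on or after the first dose. Section 2.3 of the SAP addendum notes that some subjects stayed enrolled and took study product after the Exit DBPCFC; it removes that product from the exposure and compliance summaries and does not mention episodes.

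**The concern.** An accidental ingestion can happen on any day, so a subject watched for 22 weeks has about eleven times the opportunity of one watched for 2. If mean follow-up differs between arms, events per subject differ even when the underlying rates are the same. Follow-up here is set by tolerance of dosing, which treatment may well affect, so a difference between arms is plausible.

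The numerator has its own problem. If treatment works, some exposures that would have caused a reaction will pass without one. A count that does not distinguish the two could show no difference where reactions do differ.

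Protection against accidental exposure is the program's stated goal (Protocol 1.1), and reduced vigilance during treatment is a named risk (Protocol 1.6.1). This table is the most direct summary of both.

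**Working it through.** The documents give no episode rate, so there is no plan figure to reproduce. The check asks what the formula returns when the true rates are equal.

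**Step 1: formula.** Let λ be the episode rate per subject-year, constant over time and equal in both arms. Then

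expected events per subject = λ × (mean follow-up in weeks / 52).

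λ cancels between arms:

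CPNA/placebo ratio of per-subject figures = mean CPNA follow-up / mean placebo follow-up.

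A ratio of subject-time rates would be 1.00 throughout.

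**Step 2: inputs.** From the documents: about 50 subjects randomized 1:1, so 25 per arm; follow-up of about 2 weeks (initial-escalation failure), 22 weeks (no dose reductions, upper figure), 24 + 2 = 26 weeks (escalation halted before Week 24) and 36 weeks (latest exit). Non-completion of 3 or 5 per arm comes from the sample-size section. Assumed: how CPNA subjects divide among these durations, a stop at week 12 in one pattern, and, except in the last row, all placebo subjects at 22 weeks.

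**Step 3: results.**

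| Assumed CPNA pattern | Mean CPNA weeks | Ratio to placebo |
|---|---|---|
| 3 at week 2, 22 at 22 | (6 + 484)/25 = 19.6 | 19.6/22 = 0.89 |
| 5 at week 2, 20 at 22 | (10 + 440)/25 = 18.0 | 18.0/22 = 0.82 |
| 5 at week 12, 20 at 22 | (60 + 440)/25 = 20.0 | 20.0/22 = 0.91 |
| 5 at week 2, 5 at 36, 15 at 22 | (10 + 180 + 330)/25 = 20.8 | 20.8/22 = 0.95 |
| 5 halted, followed to 26, 20 at 22 | (130 + 440)/25 = 22.8 | 22.8/22 = 1.04 |
| 5 at week 2, 10 at 36, 10 at 22 | (10 + 360 + 220)/25 = 23.6 | 23.6/22 = 1.07 |
| 10 at 36, 15 at 22 | (360 + 330)/25 = 27.6 | 27.6/22 = 1.25 |
| 5 at week 2, 20 at 22, in both arms | 18.0 in each | 1.00 |

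With 5 CPNA subjects stopping at week 2, the loss is 5 × 20 = 100 subject-weeks. Each subject extended from week 22 to 36 adds 14. The sign changes at 100/14 ≈ 7 extended subjects.

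**Step 4: numerator.** If a share f of forms records no reaction, forms exceed reactions by a factor 1/(1 − f). The documents do not give f. Over an assumed range of 0 to 50%, the factor is 1.00 to 2.00. Example with assumed counts: 10 forms in each arm, with 4 reactions on CPNA and 8 on placebo. Counting every form gives 10/25 = 0.40 per subject in both arms. Counting reactions gives 4/25 = 0.16 against 8/25 = 0.32.

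**The case against.** The strongest objection is that this is an ordinary crude summary whose formula is stated openly. Food allergy episodes are not a listed endpoint and nothing is tested. SAP 10.4 also reports the number of subjects with any episode and with a peanut episode, and it separates episodes with unscheduled visits, treatment or SAE status, which goes some way toward isolating clinically relevant reactions. SAP 10.1 summarizes treatment duration by arm, so a difference in exposure would be visible. All of this stands, and it limits the priority. It does not cure the formula: the sub-rates use the same denominator, and the reader is left to make the adjustment.

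Two stronger readings are tempting, and the documents support neither.

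- *That early stopping will be concentrated on CPNA, so the formula will make CPNA look safer.* The sample-size section assumes the same number of non-completers in each arm. Subjects halted before Week 24 are followed to about week 26, longer than the 20 or 22 weeks of dosing without reductions, and dose reductions lengthen follow-up further. Poor tolerance can therefore raise or lower mean follow-up.
- *That the SAP counts symptom-free exposures as episodes.* SAP 10.4 speaks of a safety event, and Protocol 7.2 lists consumption without a reaction as something the form captures in addition. What can be said is that no exclusion rule exists, that SAP 11.1 equates a recorded episode with an exposure, and that the blinded review does not sort reactions from non-reactions. A programmer could reasonably count every form.

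**Conclusion.** The concern holds as a weakness of definition with no predictable direction. The arm with the shorter mean follow-up has its episode rate understated relative to the other. In the patterns examined the per-subject ratio runs from 0.82 to 1.25 when the true ratio is 1.00, and there is no distortion if mean follow-up is equal. Those figures rest on a constant rate, 25 subjects per arm and assumed stopping and extension patterns; they illustrate the formula and do not forecast the result.

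The numerator is ambiguous: reaction-free peanut consumption is neither included nor excluded in terms. How much this matters depends on the share of such forms, which the documents do not give.

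Neither point affects the primary or key secondary analyses.

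**What to change.** In SAP 10.4:

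1. Report episodes per subject-year by arm with an exact Poisson 95% CI. Let both the time at risk and the counted episodes run from first dose to the Exit DBPCFC or, if there is none, to the last study contact.
2. Keep events per subject only if it is labelled crude.
3. Report reactions and reaction-free peanut consumption on separate lines, and add that sort to the blinded review in SAP 12.

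The cost is small. SAP 8.4 already derives days on study from first dose, although it summarizes them only for subjects lost to follow-up; the end date must be cut at the Exit DBPCFC where one took place. Episodes may be few, so intervals will be wide. The Poisson interval also takes episodes as independent, so repeated episodes in one subject would make it too narrow; the count of subjects with an episode, already planned, should stay beside it. Because the summary is descriptive and untested, this is a low-priority change.
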